29.4.4 Subject Accrual and Compliance

Reports of patients who meet the clinical inclusion criteria and who did and did not receive study drug will be reviewed weekly for the first 2 months of the study and then monthly thereafter to ensure adequate patient recruitment.

29.5 Quality Assurance and Auditing

All documents and data shall be produced and maintained in such a way to assure control of documents and data to protect the subject's privacy as far as reasonably practicable. The sponsor and representatives of the FDA or other regulatory authorities are permitted to inspect the study documents (e.g., study protocol, CRFs, and original study-relevant medical records/files) as needed. All attempts will be made to preserve subject confidentiality.

The study site is subject to audit by study sponsor personnel or designee for protocol adherence, accuracy of eCRFs and compliance with applicable regulations. The sponsor will communicate to the sites any patterns of non-compliance. The sponsor will work with the sites to determine any necessary corrective action, as applicable. The study protocol, data-recording procedures, data handling and study reports are subject to an independent clinical Quality Assurance audit by sponsor, its designee, or health authorities.

30.0 INVESTIGATOR RESPONSIBILITIES

30.1 General Responsibilities

- Each investigator is responsible for i) ensuring that an investigation is conducted per the signed investigator statement (Investigator Agreement/Commitment), the study protocol, and applicable regulations, ii) protecting the rights, safety, and welfare of study subjects under the investigator's care and iii) controlling drugs under investigation.
- The investigator shall assure the accuracy, completeness, legibility and timeliness of the data reported to the sponsor on the CRFs and in all required reports.
- Each investigator (or designee) is responsible for all applicable IRB requirements under 21 CFR Part 56 and ISO14155.
- Each investigator is responsible for disclosure of financial obligations/conflict of interest to the sponsor in accordance with provisions of 21 CFR Part 54.
- The study will be conducted under 21 CFR 11, 50, 54, 56, 812 and ISO14155. Investigators will be trained on their responsibilities.
- To ensure proper execution of the study protocol, each investigator will identify study coordinators for this study. Working with and under the oversight of the principal investigator, the study coordinators ensures that all study requirements are fulfilled.
- Each investigator will allow monitoring and auditing of their clinical investigation procedure(s) by the sponsor or designee.

30.2 Good Clinical Practice

ICH E6 Good Clinical Practice guidance is an international ethical and scientific quality standard for designing, conducting, recording, and reporting trials that involve the participation of human subjects.

It specifies general requirements intended to:

- Protect the rights, safety and well-being of human subjects,
- Ensure the scientific conduct of the clinical investigation and the credibility of the clinical investigation results,
- Assist Sponsors, investigators, ethics committees, regulatory authorities and other bodies involved in the conformity assessment of drugs.

The Principal Investigator of the clinical investigation shall:

- Obtain and maintain IRB/EC approval of the study.
- Ensure only appropriately trained personnel will be involved in clinical investigation.
- Maintain study records mentioned in the protocol.

- Maintain logs for study team delegation, site visit/monitoring, equipment disposition, study team training, subject recruitment and enrollment.
- Evaluate all adverse events and determining whether the study is safe to continue.
- Allow the Sponsor to conduct periodic monitoring of study activities to ensure GCP compliance.

The Sponsor shall ensure existence and record of all necessary compliance documents, and will conduct monitoring visits to ensure appropriate conduct of the study.

30.3 Provisions to Protect the Privacy Interests of Subjects

Per FDA guidance, a waiver of informed consent may be used for clinical research involving minimal risk. This study has received a waiver of informed consent for the entire study through an approved UCLA IRB application.

Prior to the start of data collection or subject enrollment, the Investigator must provide documentation of IRB approval of the study protocol.

All subjects will be monitored closely throughout the study. The following measures will be taken to ensure the privacy of subjects:

- Subject data will be fully de-identified via an honest broker. Only the honest broker will have access to identifiable patient data for the study.
- Access to the documents and data will only be made to the Investigators and study staff in the study.
- The confidentiality of these documents will be protected to the extent provided by the law.

30.4 Maintenance and Retention of Study Records

The PI is required to maintain adequate and accurate study records in accordance with Sponsor requirements.

The PI shall have the following record keeping and reporting obligations:

preparation and maintenance of written records in accordance with laws, regulations and good clinical practice; a Study manuscript, which would be appropriate for submission to a peer reviewed journal, provided to Merck within one-year from the final subject being examined or receiving an intervention for the purposes of final collection of data of the Study regardless of the Study results;

preparation and submission of periodic progress reports every three (3) months via the Merck grant management web site or, if the Parties can agree to an alternative format, such format as the Parties have otherwise mutually agreed upon in writing (failure to provide progress reports may result in immediate termination of this Agreement); and

A final study report summarizing the Study results and conclusions reached by Institution within a reasonable time after completion of the Study but in no event longer than six (6) months after completion of the Study. The final study report shall be made of descriptive data, tables, and data listings, and contain all relevant adverse experiences as a line listing or

table. Any Study subject level data submitted to Merck will only be coded with a number and no other personal identifiers such as birth date or Study subject initials

30.5 Institutional Review Board Approval

Institutional Review Board (“IRB”) approval of study protocol and ICF is required prior to study commencement under 21 CFR Part 56. The sponsor’s justification of the non-significant risk determination of the study and any supporting information, as necessary, will be provided to the IRB under 21 CFR 812.2(b). Clinical investigators must also obtain renewal of IRB approval throughout the duration of the study. Clinical investigators are responsible for fulfilling any conditions of approval imposed by the reviewing IRB, such as regular reporting, study timing, etc. Clinical investigators will provide the study sponsor with copies of such approvals and reports.

30.6 Required Documentation from Sites

At a minimum, the following documents will be stored by the study site:

- IRB study approval letter
- Fully executed clinical trial agreement (CTA)
- Investigator agreement/commitment for the participating investigator(s)
- Financial disclosure form for the participating investigator(s)
- Curriculum vitae (CV) for the participating investigator(s)
- Current medical license for the participating investigator(s)
- Principal investigator protocol acknowledgement form

31.0 PROTOCOL AMENDMENTS

Any changes made to the clinical investigational plan/study protocol will be documented by way of an amendment. The Investigator shall not make any changes to the protocol without Sponsor approval and documented approval from the IRB. The PI will retain the IRB approval letter and approved protocol as confirmation that the protocol amendment was approved.

32.0 SUSPENSION OR TERMINATION OF STUDY SITE

The Sponsor can suspend or pre-maturely terminate the PI’s and study site’s participation in the study, particularly if the Sponsor finds serious non-compliance by the PI or site, and if such non-compliance was not resolved in a timely and appropriate manner. The Sponsor will document the decision to suspend or terminate the investigation in writing. A suspended study site cannot enroll new subjects.

If the Sponsor determines that the study site’s compliance to GCP and federal regulations to be inadequate at any point during the study, and the Sponsor moves to suspend or terminate the study site, the Sponsor will provide notification in writing to the principal investigator and IRB as necessary. The study site is eligible for re-instatement upon correction of

any findings and any open action items prior to the suspension, and provides a written guarantee that the same non-compliance will not re-occur in the future. Site can only resume patient enrollment upon patient enrollment upon receiving written notification of re-instatement from the Sponsor and/or the IRB.

33.0 TERMINATION OF CLINICAL INVESTIGATION/STUDY

The clinical investigation may be terminated if Sponsor determines that an unanticipated adverse drug effect presents an unreasonable risk to the subjects, obtaining new scientific knowledge that shows the study is no longer valid, insufficient recruitment of subjects, or at the discretion of the study Sponsor, IRB, or other regulatory body. In the event Merck or Institution believes that immediate termination is necessary due to its evaluation of risks to enrolled subjects, Merck or Institution may terminate the study immediately.

34.0 PUBLICATION AND DATA SHARING POLICY

All Study data and results will be owned by Institution. Institution agrees that all reports and compilations of data required to be delivered to Merck under the Protocol or this Agreement, and all Study data and results (excluding protected health information, patient medical records and all original source documents) as contained therein generated in the course of the Study ("Study Reports") may be used fully by Merck for any legitimate business purpose without any additional payments being made to Institution, subject to applicable regulations and laws. Institution does not promise any particular results from the Study and makes no representation or warranty of any kind, expressed or implied, with respect to the Study results. Merck agrees not to publish or otherwise disclose the Study Reports and any portion of the research data and results contained therein generated during the course of the Study until Institution's publication or presentation of the Study results in accordance with this Article 9, or eighteen (18) months following completion of the Study or termination of this Agreement, whichever occurs first. Notwithstanding anything to the contrary, Merck may disclose the research data and results to applicable federal, state or local health authorities provided if such disclosure is prior to Institution's publication Merck shall use reasonable efforts to disclose such research data and results contained therein confidentially and shall give Institution reasonable advance written notice of the required disclosure. Institution agrees not to provide any competing commercial third party with access to or with the right to use the data or results for any purpose until publication as set forth herein without the written permission of Merck, which shall not be unreasonably withheld.

36.0 APPENDIX A - LIST OF STUDY INVESTIGATORS

Sites and investigators subject to IRB approval and subject to change without requiring protocol amendment.

Principal Investigator	[name] Dept. of Anesthesiology and Perioperative Medicine Ronald Reagan Hospital, University of California Los Angeles Email: [contact]
Other Site Investigators	[name]
	[name]
	[name] PhD
	[name]
Study Coordinators	[name]
	[name]

Statistical Analysis Plan

Variables/Time Points of Interest

Overall a variety of variables may be used for patient risk stratification, or creation of the propensity score. The majority of these have standard definitions and are listed above. The list below includes key variables used as inclusion criteria and or outcomes.

- PACU Discharge Time (primary endpoint): The duration in minutes from patient arrival in PACU until the ready for discharge order is placed by the anesthesiologist. This captures the time until they are clinically ready for discharge and eliminates noise such as the availability of beds that might effect actual discharge time
- Incidence of oxygen saturation <90%: A binary variable indicating if the patient had any oxygen saturations below 90% from arrival in PACU until being marked for discharge
- Incidence of oxygen saturation <95%: A binary variable indicating if the patient had any oxygen saturations below 95% from arrival in PACU until being marked for discharge
- Duration of supplemental oxygen use in PACU: The total time in minutes that a patient received supplemental oxygen from arrival in PACU until being marked for discharge
- Reintubation rate: The incidence of patients who required reinsertion of an endotracheal tube after the patient was extubated in the OR. This includes patients who were reintubated in the PACU or subsequently after PACU discharge
- Unplanned Upgrade of Care: The incidence, defined as a binary variable, of patients who were transferred to an ICU after being admitted to a non-ICU setting.
- Obstructive Sleep Apnea (OSA): The presence of obstructive sleep apnea based upon previous structured data in the electronic medical record (EMR) such as prescriptions for CPAP, medical history and the anesthesiologist's preoperative note.
- Preexisting respiratory disease: The presence of obstructive or restrictive lung disease as defined based on the structured data in the EMR such as previous PFT results, previous medication and previous diagnoses. For analysis purposes patients will be divided into low, medium and high risk groups based on the extent of their disease.

Statistical Methods:

All analysis will be performed by the study team at UCLA.

Retrospective analysis: In order to assess the change in time to readiness for PACU discharge and postoperative respiratory dysfunction (duration of oxygen saturation below 90%) after the introduction of sugammadex we will construct two models. First, we will utilize propensity score matching (PSM) to adequately risk balance the patients pre/post sugammadex introduction. We will use the nearest-neighbor PSM approach and start with a caliper of width equal to 0.2 of the standard deviation of the logit of the propensity score. We will assess balance of the covariates pre/post intervention by computing standardized mean differences (SMD) for each variable and will use the rule of thumb “SMD less than 0.1” to indicate adequate balance. Finally, we will also construct a table of patient characteristics pre/post matching to see how well the algorithm balanced the patients. After adequate balance is observed, we will compare our outcomes of interest between pre/post periods using a linear (or log-linear) model for time to readiness and logistic regression for our binary outcome (postoperative respiratory dysfunction) using the propensity matched dataset. An interrupted time-series (also known as segmented regression) analysis as described by Wagner will be conducted for each outcome to estimate the pre-intervention time trend, immediate impact of intervention (change-point), as well as reliably estimating the slope change after the intervention. All estimates of interest from these models will be summarized with p-values and 95% confidence intervals.

Statistical analyses will be performed using R V3.5.1 (Vienna, AU) using the “Match” package for propensity score matching and p-values <0.05 will be considered statistically significant.

Prospective analysis: The prospective analysis will largely follow a similar framework however we will focus on the primary and secondary outcomes as described above and will use a one year period prior to implementation as our baseline.

Power/Sample Size:

Sugammadex was introduced into clinical practice at UCLA in May of 2016, thus we have well more than one year of data prior to and after sugammadex introduction. As a result, the power analysis and sample size discussion is roughly the same for the retrospective and prospective portions of this study.

Over the previous one year period, approximately 6,5000 patients received general anesthesia with the use of either rocuronium or vecuronium. Given that our surgical volumes are stable we would expect the sample size for the prospective portion of our study to be roughly the same. The table below contains the risk stratification for this group.

To determine the study power, we analyzed the incidence of the primary and secondary outcomes for our historical population. Because there is no current pathway, we are unable to explicitly model the power

for pathway compliance, however the power for the primary outcome as well as secondary outcomes were calculated.

In order to determine our power for the study variables patients were separated into low, medium, and high-risk groups. Low risk patients were those who had no prior documentation of OSA or respiratory disease prior to surgery. Medium risk patients were those with either OSA or respiratory disease and high risk patients were those with both diseases. It is important to note that this classification is significantly simplified as compared to the analysis that will be performed for either the retrospective or prospective studies as it fails to account for key factors such as severity of illness. Nonetheless we believe that these simplifications have the effect of underestimating the potential power and thus the below serves as a conservative estimate.

Given 1 year of data, we observed an overall average PACU discharge time of 152.54 minutes (SD=623.86). With one year of post-data, we are adequately powered (90%) to pick up a reduction in PACU discharge time as small as 24.84 (two-sample t-test, alpha=0.05). Since the current difference in PACU discharge time between low and high risk groups is 67.52 (subtracting 216.62

149.10, see table), we feel the 24.84 minimally detectable difference gives us a great chance of detecting a meaningful difference.

Given 1 year of data (pre-period), we observed the rate of patients with any time SpO₂<90% was 4.6% (574/12,467). With one year of post-data, we are adequately powered (90%) to pick up a reduction in this rate if it decreases to around 3.8% in the post (chi-square test, alpha=0.05). Since the current difference in patients with any time with SpO₂<90% between low and high risk patients is 5.2% (subtracting 9.2%-4.0%), we feel the minimally detectable difference of 0.8% (4.6%-3.8%) is feasible.

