25.0 POWER ANALYSIS AND SAMPLE SIZE DETERMINATION

25.1 Retrospective analysis

In order to assess the change in time to readiness for PACU discharge and postoperative respiratory dysfunction (duration of oxygen saturation below 90%) after the introduction of sugammadex we will construct two models. First, we will utilize propensity score matching (PSM)¹⁴ to adequately risk balance the patients pre/post sugammadex introduction (variables mentioned in section 2.4). We will use the nearest-neighbor PSM approach and start with a caliper of width equal to 0.2 of the standard deviation of the logit of the propensity score (as described by Austin¹⁵). We will assess balance of the covariates pre/post intervention by computing

standardized mean differences (SMD) for each variable and will use the rule of thumb “SMD less than 0.1”¹⁶ to indicate adequate balance. Finally, we will also construct a table of patient characteristics pre/post matching to see how well the algorithm balanced the patients. If individual covariates are not adequately balanced with the default propensity score matching algorithm, we will try different matching parameters until adequate balance is achieved (e.g. change the caliper size for what we consider a match and/or run a more advanced propensity score model including interaction or squared terms).

After adequate balance is observed, we will compare our outcomes of interest between pre/post periods using a linear (or log-linear) model for time to readiness and logistic regression for our binary outcome (postoperative respiratory dysfunction) using the propensity matched dataset. An interrupted time-series (also known as segmented regression) analysis as described by Wagner¹⁷ will be conducted for each outcome to estimate the pre-intervention time trend, immediate impact of intervention (change-point), as well as reliably estimating the slope change after the intervention. All estimates of interest from these models will be summarized with p-values and 95% confidence intervals.

Statistical analyses will be performed using R V3.5.1 (Vienna, AU) using the “*Match*” package for propensity score matching and p-values <0.025 (for our two primary outcomes) will be considered statistically significant utilizing the Bonferroni adjustment (0.05/2).

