At this point, we estimate that the pathway will recommend sugammadex for all patients in the medium or high-risk groups as well as some patients in the low risk group (i.e. those patients requiring deep neuromuscular blockade to facilitate surgical conditions such as robotic procedures, free flap cases and others). Given the large number of patients, Merck would supply one vial of study drug for each patient. Thus the total amount of study drug would be no more than 6,500 patients for the one year intervention time.

Given 1 year of data, we observed an overall average PACU discharge time of 152.54 minutes (SD=623.86). With one year of post-data, we are adequately powered (90%) to pick up a reduction in PACU discharge time as small as 27.04 (two-sample t-test, alpha=0.025). Since the current difference in PACU discharge time between low and high risk groups is 67.52 (subtracting 216.62-149.10, see table), we feel the 27.04 minimally detectable difference gives us a great chance of detecting a meaningful difference.

Given 1 year of data (pre-period), we observed the rate of patients with any time SpO2<90% was 4.6% (574/12,467). With one year of post-data, we are adequately powered (90%) to pick up a reduction in this rate if it decreases to around 3.7% in the post (chi-square test, alpha=0.025). Since the current difference in patients with any time with SpO2<90% between low and high risk patients is 5.2% (subtracting 9.2%-4.0%), we feel the minimally detectable difference of 3.7% (4.6%-3.8%) is feasible.

Table 2.

	suppl O2, mean (SD)	PACU disch. Time, mean (SD)	Reintubation, freq (%)	Unplanned upgrade, freq (%)	SpO2<90%, freq (%)	SpO2<95%, freq (%)
OVERALL(n=13,277)	74.81 (241.82)	152.54 (623.86)	89 (0.7%)	138 (1.0%)	574 (4.6%)	6510 (52.3%)
low (n=9,841)	74.48 (280.55)	149.10 (599.78)	63 (0.6%)	111 (1.1%)	372 (4.0%)	4603 (50.0%)
medium(n=2,997)	74.98 (95.67)	154.43 (536.58)	23 (0.8%)	22 (0.7%)	164 (5.8%)	1658 (58.8%)
high (n=439)	79.54 (88.44)	216.62 (1321.46)	3 (0.7%)	5 (1.1%)	38 (9.2%)	249 (60.9%)
Smallest detectable difference (90% power)	9.61	24.84	0.4%	0.4%	3.8%	50.3%

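### The protocol requires p<0.025 and the SAP p<0.05 for the same analysis, and the documents disagree on whether there are one or two primary outcomes

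*Combined protocol and SAP*

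**What the plan says.** **Threshold.** Protocol section 25.1 ends its analysis paragraph with "p-values <0.025 (for our two primary outcomes) will be considered statistically significant utilizing the Bonferroni adjustment (0.05/2". The matching paragraph in the SAP (Statistical Methods), with the same matching method, models and software, ends with "p-values <0.05 will be considered statistically significant" and mentions no adjustment. Both sentences belong to the retrospective analysis. Section 25.2 and the SAP's prospective paragraph give no threshold; they refer back to broadly the same framework.

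**Number of primaries.** The Protocol Summary lists two numbered primary objectives (time to fitness for discharge, and hypoxemia below 90%), and section 25.1 counts two. The Summary's Study Endpoints, section 10.0 and the SAP's variable list attach the primary label to PACU discharge time alone. Section 26.0 and the SAP's Power/Sample Size text use the singular, primary outcome.

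**Power text.** Section 26.0 gives a "reduction in PACU discharge time as small as 27.04 (two-sample t-test, alpha=0.025" and a post-period rate of 3.7% for SpO2<90%, also at 0.025. The SAP gives a "reduction in PACU discharge time as small as 24.84 (two-sample t-test, alpha=0.05" and a "reduction in this rate if it decreases to around 3.8% in the post (chi-square test, alpha=0.05".

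**Table 2.** In section 26.0 the last row, "Smallest detectable difference (90% power", states no alpha and shows 24.84 and 3.8%, next to text giving 27.04 and 3.7%. The same section speaks of a "minimally detectable difference of 3.7% (4.6%-3.8%) is feasible"; the SAP's counterpart is a "minimally detectable difference of 0.8% (4.6%-3.8%) is feasible".

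**The concern.** The two documents give different decision rules for the same tests, and no statement of precedence resolves them. If the choice between 0.025 and 0.05 is still open when the p-values are known, the result can drive it, and the analysis is done by the study team itself.

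The number of primaries has to be settled at the same time, because it determines whether an adjustment is needed at all. Ranking the protocol above the SAP would not be enough: the protocol disagrees with itself on whether there are one or two.

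**Working it through.** **Inputs.** SD of PACU discharge time 623.86 min and overall n = 13,277 (section 26.0 and its Table 2); SpO2<90% baseline 574/12,467 = 4.6% (section 26.0); SD of supplemental oxygen time 241.82 min and SpO2<95% baseline 52.3% (Table 2). Power is 90% and tests are two-sided. Equal pre and post periods are assumed, as section 26.0 expects stable volumes.

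**1. PACU discharge time.** SE = 623.86 × √(2/13,277) = 7.657. Detectable difference = (z for alpha + 1.2816) × SE.
- Alpha 0.05: (1.960 + 1.2816) × 7.657 = 24.82 min; the SAP prints 24.84.
- Alpha 0.025: (2.2414 + 1.2816) × 7.657 = 26.98 min; the protocol prints 27.04.
- Crossing the alphas fails: 24.84 min has 84.2% power at 0.025, and 27.04 min has 94.2% at 0.05.

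**2. SpO2<90%.** Pooled-variance test of two proportions, 12,467 per period, baseline 4.6%, solved for the post-period rate p2 at which Φ{[p1 − p2 − z√(2p̄(1−p̄)/n)] / √[(p1(1−p1) + p2(1−p2))/n]} = 0.90.
- Alpha 0.05: 3.78%, a difference of 0.82 points; the SAP prints 3.8% and 0.8.
- Alpha 0.025: 3.71%, a difference of 0.89 points; the protocol prints 3.7%.
- Crossed, power is 81.8% (3.8% at 0.025) and 94.6% (3.7% at 0.05).

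Each document's power text therefore follows its own alpha.

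**3. Table 2, last row.**

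| Cell | Printed | At 0.05 | At 0.025 | Kind of figure |
|---|---|---|---|---|
| Supplemental oxygen | 9.61 | 9.62 | 10.46 | difference |
| PACU time | 24.84 | 24.82 | 26.98 | difference |
| SpO2<90% | 3.8% | 3.78% | 3.71% | post-period rate |
| SpO2<95% | 50.3% | 50.25% to 50.31% | 50.07% to 50.14% | post-period rate |

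(The SpO2<95% ranges use 12,467 and 13,277 per period.) These four cells are at alpha 0.05, and two of them are rates under a row label that says difference. The phrase in the section 26.0 text has the same fault: 4.6% − 3.8% is 0.8 points, and 3.7% is the post-period rate at the other alpha. At alpha 0.025 the difference is 4.6% − 3.7% = 0.9 points.

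**4. Where the rules disagree.** The critical |z| is 1.960 under the SAP and 2.2414 under the protocol. For scale only, in an unmatched two-sample z-test with 13,277 per period, observed reductions from 1.960 × 7.657 = 15.0 min to 2.2414 × 7.657 = 17.2 min fall between the rules. The planned analysis is a matched linear or log-linear model, so this band is an illustration.

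**5. Family-wise error,** if there are two primaries, either suffices, and each has one decisive test:
- 0.05 each: at most 0.05 + 0.05 = 10%; 1 − 0.95² = 9.75% if independent.
- 0.025 each: at most 5%; 1 − 0.975² = 4.94% if independent.
- One primary at 0.05: 5%.

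**The case against.** **Each document read alone can be defended.** The SAP labels one primary and tests at 0.05; section 25.1 counts two and halves the alpha. This stands to the extent that 0.05 is not wrong in itself. The SAP's one-primary reading is thin, however: it rests on a label and a singular noun, while the SAP builds models for both outcomes and its power text covers exactly those two.

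**Sidedness might explain the split.** One-sided 0.025 gives 24.82 min, the same as two-sided 0.05. But the protocol's 27.04 min fits only a two-sided 0.025 test, so this fails.

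**The disputed band is narrow.** In the same simple model, p lands in it with probability 90.05% − 84.20% = 5.8% if the true difference is 24.84 min, and 4.0% if it is 27.04 min. The maximum is about 11%, near 16 min. That is a fair limit on practical reach. It does not excuse a success rule that depends on which document is opened.

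**Stronger readings that a reader might infer.**
- That the SAP's rule inflates type I error to nearly 10%. This needs two primaries with either sufficing, and the documents settle neither.
- That the protocol's rule secures 5%. Each outcome also gets a segmented regression, with p-values for level and slope change, so halving alpha over two outcomes gives that bound only if one test per outcome is decisive.
- That conflicting thresholds are printed for the prospective analysis. They are not; they reach it by reference only.

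**Conclusion.** The contradiction is real and has to be resolved before analysis. For an outcome that the protocol calls primary, p from 0.025 to below 0.05 (0.025 itself included) is significant under the SAP and not under the protocol. Both rules were carried into the power calculations, so this is not a misprint in one sentence.

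The documents do not show which rule is right. With a single primary, 0.05 is valid. With two primaries, either sufficing and one decisive test each, 0.05 per outcome allows up to 10% family-wise error against 5% at 0.025. The reproduced power figures rest on about 12,500 to 13,300 patients in each period. Whether the prospective phase will reach that number is a separate question and is not part of this point.

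**What to change.** Before analysis, settle the number of primaries and the alpha together. Put one rule in both documents and state that it governs the retrospective and the prospective analysis. Name the one decisive test per primary outcome, for example the matched comparison with the segmented regression as supportive. The choice between the two options is the sponsor's.

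**Option A: two primaries, each at p<0.025.**
- Change the SAP threshold, and state whether success needs either outcome or both.
- Label the incidence of SpO2<90% as primary in the Summary's Study Endpoints, section 10.0 and the SAP's variable list; make primary outcome plural in section 26.0 and the SAP power text.
- In section 25.1 and SAP Statistical Methods, respiratory dysfunction is described as time spent below 90% and then treated as binary. Replace the former with the binary incidence defined in section 10.0 and the SAP.
- Set the SAP power text to 27.04 min and 3.7% (0.9 points) at alpha 0.025, and move the two primary cells of Table 2 to match.

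**Option B: one primary, PACU discharge time, at p<0.05.**
- Change the Primary Objective list and the section 25.1 threshold.
- Return the section 26.0 text to 24.84 min and 3.8% (0.8 points) at alpha 0.05.

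**Under either option.**
- Correct the section 26.0 phrase that calls 3.7% a difference.
- In Table 2's last row, print the alpha for each cell; under Option A the primary and secondary cells would differ.
- In that row, either show differences (0.9 or 0.8 points for SpO2<90%, about 2 points for SpO2<95%) or label those cells as detectable post-period rates.
- State that the figures assume about 12,500 to 13,300 patients per period.

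**Cost.** A SAP revision and a protocol amendment, which under section 31.0 needs sponsor and IRB approval; no new data. The downside of A is a slightly less favourable detectable difference in the SAP (27.04 instead of 24.84 min). The downside of B is that SpO2<90% is no longer primary.
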